Schizophrenia is one of the leading causes of disability worldwide and the burden of this disease on individual health and society at large is substantial (1). While new pharmacological treatments are emerging, no treatment for schizophrenia has been found to rival the efficacy of clozapine (2-16). Yet, the number of people with schizophrenia who are prescribed clozapine nationally is <5%, despite its recommended use in about 30-50% of people with treatment-resistant schizophrenia (17, 18). Arguably, clozapine is one of the most underutilized evidence-based treatments in psychiatry and optimization of its use could drastically improve patient outcomes and lower treatment costs (19-21). Many barriers contribute to clozapine underutilization; however, our pilot data and data from others show that lack of prescriber competence to use clozapine and challenging logistics for absolute neutrophil count (ANC) monitoring are two of the greatest barriers to

CHAMPION PROTOCOL

clozapine use (22-25). Further, pilot data shows that prescriber self-reported competence in using clozapine correlates with their prescription of clozapine. Therefore, without improving competence, changes in prescribing of clozapine are unlikely to occur.

In the last 15 years, a unique, structured and empirically validated tele-mentoring model has emerged called Project ECHO (Extension for Community Healthcare Outcomes). ECHO is a “hub” and “spoke” sharing network led by an expert academic team (the “hub”) that uses multipoint video-conferencing to conduct virtual clinics with non-expert prescribers (the “spokes”) located in areas outside the academic hub site. The use of ECHO has been shown to significantly improve best-practice specialty care in sites that lack expertise in a variety of disease states (26, 27). Importantly, multiple studies have established its efficacy in improving prescriber competence, the “target mechanism” we hypothesize to be linked to increased clozapine prescribing (26, 28-30).

In a randomized controlled design with approximately 26 biweekly sessions over 12 months, we propose to test the effectiveness of an ECHO-based intervention for improving the use of clozapine in people with treatment-resistant schizophrenia. The sessions will include: 1) active dissemination of knowledge and information by an expert “hub” followed by 2) clozapine case presentations and vignettes submitted by the “spokes”.

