This intervention, *Clozapine CHAMPION-ECHO (Center for Help and Assistance for Maryland Prescribers-Improving Outcomes Network using Extension for Community Healthcare Outcomes*, will be referred to as “CHAMPION” throughout the application. To minimize ANC monitoring barriers and maximize recruitment, we will provide Food and Drug Administration (FDA)-approved ANC point of care (POC) monitoring devices to all study sites, including those in the control condition (the PI and clinical team has used this previously). We will enroll at least 300 prescribers and additional clinical team members (up to 300) from approximately 60 outpatient mental health clinics (OMHCs) and other treatment sites. Individual prescribers can also enroll. Approximately half the sites/individuals will be randomized to CHAMPION and half randomized to enhanced treatment as usual (ETAU).

SPECIFIC AIMS

Aim 1:

To determine the effect of 12 months of CHAMPION exposure on: a) the clozapine prescribing practices of prescribers/clinical team; and b) the persistence of their patients use of prescribed clozapine. Hypothesis 1: Relative to the prescribers randomized to ETAU, prescribers randomized to CHAMPION will significantly increase the proportion of patients in their care who are prescribed clozapine as assessed using Maryland Medicaid prescription data. Hypothesis 2: For patients who are prescribed clozapine, the patients of prescribers randomized to CHAMPION will exhibit significantly greater persistence to clozapine treatment compared to patients of prescribers randomized to ETAU.

Aim 2:

To determine the effect of 12 months of CHAMPION exposure on prescriber knowledge and self-reported competence of prescribing clozapine and how those mechanisms of change are associated with increased clozapine prescribing and persistence of clozapine use. Hypothesis 3: Relative to the prescribers randomized to ETAU, prescribers randomized to CHAMPION will demonstrate significantly increased levels of clozapine knowledge and self-reported competence. Hypothesis 4: Prescriber self-reported competence will mediate the effect of CHAMPION on clozapine prescribing and persistence.

Exploratory Aims:

CHAMPION PROTOCOL

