The Hilltop institute maintains private and secure files and will be transferring requested data to the University of Maryland School of Medicine, Division of Services Research only through a secure file transfer protocol, Accellion. All data kept at the Division of Services Research are strictly confidential and secure.

CHAMPION PROTOCOL

Data Elements will include:

We will begin to collect data retrospectively for one year prior to the start of the CHAMPION intervention. This is slated to occur in approximately June of 2021 for the period of December of 2019 onward. We will collect data until one year after the CHAMPION ends or around June of 2023. Thus, we will be examining Medicaid data for a period of December 2019 to December of 2023 approximately.

The elements we will be collecting include collecting Maryland Medicaid recipient data for those who are over the age of 18. We are asking for data on those with a 295 diagnosis so we can examine antipsychotic and clozapine treatment. We anticipate approximately 350,000 antipsychotic prescriptions and 75,000 clozapine prescriptions annually.

We will have participant ID to link records for examining adherence and persistence. Thus, we will have Medicaid enrollment and demographic data, inpatient and outpatient claims data, other professional fee services, pharmacy data and provider information. The provider linkage is needed to link the knowledge and competence testing to rates of prescribing. Specifically, this includes:

Date of Service	Dates for prescription
Drug Name	Identification of antipsychotic name
Drug Formulation	Route of administration of type of antipsychotic
Strength	Dose of the Antipsychotic
Quantity	Number dispensed
Participant's Medicaid ID	Identification number of the patient
Claims data	Inpatient and Outpatient services for 295 diagnosis
Age	Age of patient
Zip code	Zip code where living
Race	Race
Prescriber ID	Prescriber identification number
Prescriber zip code	Zip code of where the prescriber resides
Prescriber county	County where the prescriber resides

HMIS Data and Security

CHAMPION PROTOCOL

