Hypothesis 3: Although the variables for hypothesis 3 are normally distributed, the specifications are the same and the power calculations are identical to those noted above. Based on literature described in Approach section 10 above, we anticipate changes in knowledge and competence to be large ($>.8$).

Hypothesis 4: Using the values above and the SAS macro from O'Rourke and MacKinnon (14), the power to detect indirect effects (mediation) will be greater than .80 when using the bias corrected bootstrap procedure when paths a and b are at least 0.3 (small to medium effects anticipated).

Statistical Analyses Overview

All data will be screened for errors using frequency and contingency tables and univariate and bivariate plots before formal analysis. These informal plots and summaries will allow us to be cognizant of data distribution characteristics before building regression models. We anticipate that our dependent variables will either have a distribution that is relatively bell-shaped or can be transformed to be relatively bell-shaped. Site will be included in all models as a random effect. Prescriber is nested within intervention arm, by design, and will be specified as a random effect in all analyses that include patient level data. The intercept will be designated as random to account for the non-independence across time point when appropriate. SAS PROC MIXED or GLIMIX will be used for the analyses described below (15).

CHAMPION PROTOCOL

Missing Data

All analyses will be conducted within an ITT framework. As described above, missing data for hypotheses 1 and 2 will be limited due to the use of Medicaid prescription records for those outcomes. For hypotheses 3 and 4, we will compare the baseline characteristics of the prescribers/clinical team who drop out prior to completing the 12-month assessment to those prescribers/clinical team who do complete the assessment. If necessary, we will investigate how estimates/results change over a range of several plausible assumptions regarding the missing mechanism together with multiple imputations to most accurately capture existent random variability.

Multiple Comparisons

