Transformations will be used if necessary. They will be measured at two time points (baseline and end of the 1-year CHAMPION). A General Linear Mixed Model (Proc MIXED) will be used to estimate the effects of the two groups on change in knowledge and competence with site as a random effect. The test of hypothesis 3 will operationally be the test of whether the coefficient of the CHAMPION/ETAU condition term is significantly greater than zero (two-sided test) at the post CHAMPION time point controlling for baseline. In exploratory analyses, we will examine individual competence scores related to outcomes as above while controlling for multiple comparisons.

Specific Aim 2, Hypothesis 4: *Prescriber self-reported competence will mediate the effect of the CHAMPION on clozapine prescribing and persistence.* A separate model will be used for each outcome. The independent variable will be group assignment, the dependent variable will be rate of clozapine prescribing during the year following CHAMPION and the persistence of clozapine episodes, and the mediator will be the overall self-reported competence score (0-100 mm VAS) measured at 12 months, controlling for baseline. We will use the product of coefficients approach to test mediation. The rationale behind this method is that mediation depends on the extent to which the independent variable changes the mediator (i.e., path a), and the extent to which the mediator affects the outcome variable (i.e., path b). The PROCESS (17) macro for SAS will be used to generate 95% bias corrected confidence intervals for the relative indirect effects and other parameters.

Exploratory Analyses

We will examine the role of race in moderating the effects of CHAMPION. To determine whether there was differential benefit of the program for the AA patients, race and interaction terms (time by race) will be added to the models described above. Despite our previous work, it is possible that increases in prescribing will not occur similarly between AA and Caucasian patients, however, we will use data collected to adapt future iterations of the topics related to AA if we do not see similar improvements in prescribing. Specifically, we will examine the two competence questions related to AA and ascertain the relationship of these specific measures to prescribing for AA and Caucasian patients. We will also look at other variables by site and patient that may contribute to outcomes and will analyze the other clinicians and examine.

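### Hypothesis 4 leaves baseline undefined and does not name the prescriber's t=1 clozapine rate, so prior prescribing habit can be credited to competence as mediation

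*Combined protocol and SAP*

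**What the plan says.** The analysis paragraph for Specific Aim 2, Hypothesis 4 takes arm as the independent variable. For the outcomes, "the dependent variable will be rate of clozapine prescribing during the year following CHAMPION and the persistence of clozapine episodes", with a separate model for each. It then states that "the mediator will be the overall self-reported competence score (0-100 mm VAS) measured at 12 months, controlling for baseline". The method is given as "We will use the product of coefficients approach to test mediation", with bias-corrected 95% intervals from PROCESS. The paragraph lists no other covariate, no confounder set and no sensitivity analysis. General rules elsewhere add a random site effect (Statistical Analyses Overview) and control for whether randomisation was by site or by individual (Multiple Comparisons).

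Four other places bear on this:

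- The opening background section says that "pilot data shows that prescriber self-reported competence in using clozapine correlates with their prescription of clozapine".
- Primary Outcomes, item a, defines the clozapine rate for the 12 months before the study as well as during and after it, so the t=1 rate is available.
- The Hypothesis 1 analysis compares arms at t=3 after adjusting for baseline. There the term refers to the outcome.
- Specific Aims, Aim 2, covers both knowledge and competence and asks "how those mechanisms of change are associated with increased clozapine prescribing and persistence of clozapine use". The data-elements section adds: "The provider linkage is needed to link the knowledge and competence testing to rates of prescribing".

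**The concern.** Randomisation protects the path from arm to competence (path a). It does not protect the path from competence to prescribing (path b), which is an observational comparison among prescribers. A prescriber who has always used more clozapine may report higher competence at 12 months and also prescribe more in the follow-up year. That yields a positive path b even if competence changes nothing.

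Adjusting for one baseline VAS removes this only to the extent that the VAS captures the link between habit and competence. The t=1 rate measures habit directly, is already held, and is not named in the model. At stake is the trial's statement about mechanism: mediation by competence could be reported when part or all of the indirect effect is prior habit. Hypotheses 1 to 3 are not affected.

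**Working it through.** **The plan's own figure.** For Hypothesis 4 it states that "the power to detect indirect effects (mediation) will be greater than .80" "when paths a and b are at least 0.3 (small to medium effects anticipated"). Inputs from Power, Hypothesis 1: N=254, 4 to 5 prescribers per site, ICC .01, alpha .05.

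- Design effect: 1 + (4.5 − 1) × .01 = 1.035. Effective N: 254/1.035 = 245.4.
- Standardised paths: path a Φ(.3√245.4/√(1 − .09) − 1.96) = Φ(2.97) = .998; path b Φ(.3√245.4 − 1.96) = Φ(2.74) = .997; joint power .995. The stated figure is reproduced.
- Path a as a 0.3 SD difference between arms: Φ(.3√(245.4/4) − 1.96) = Φ(.39) = .65; joint power .65. It is not reproduced on this reading, and the plan does not state the scale.

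Either way, this is power for a real indirect effect. It says nothing about how often mediation is declared when path b is confounded.

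**Size of the spurious path.** The documents give no confounder strengths, so all values here are assumptions in SD units, with no true competence effect. Let r be the correlation of habit with baseline competence, g the habit effect on 12-month competence given baseline competence, and s the habit effect on the t=3 rate. Path a is .8, and the residual variance of 12-month competence is .6. Adjusting for arm and baseline competence only:

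spurious b = s·g·(1 − r²) / [.6 + g²·(1 − r²)]

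Example with r=.3, g=.2, s=.5: .5 × .2 × .91 / (.6 + .04 × .91) = .091/.6364 = .143. The spurious indirect effect is .8 × .143 = .114.

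The table takes r .3 to .5 and s .5 to .7 for the indirect effect. The false-mediation columns use r=.4, s=.6, N=254 and 2,000 simulated trials.

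| g | Spurious indirect effect | False mediation as planned | With an error-free t=1 rate |
|---|---|---|---|
| 0 | 0 | 5% | 4–6% |
| .1 | .05–.08 | 18% | 4–6% |
| .2 | .10–.16 | 56% | 4–6% |
| .3 | .14–.22 | 88% | 4–6% |

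The bias is zero when g=0, that is, when baseline competence already absorbs the link.

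**Measurement error alone.** A residual link can arise simply because the baseline VAS is noisy. A second simulation assumes only that.

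- N: 278 prescribers (HMIS Data and Security) × 85% (Power, Hypothesis 1) = 236.
- Path a 0.8 SD; VAS reliability .70 to .85; clozapine-rate reliability .70; habit stable; no competence effect.
- True habit-competence correlations .3, .5 and .7. The observed baseline correlation is the true value × √(product of reliabilities). For .3: .3√(.70 × .70) = .21 and .3√(.85 × .70) = .23. Likewise .35–.39 and .49–.54.
- Decision rule: both paths significant by least squares, as a stand-in for the PROCESS interval.

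False mediation under the planned model, by the 12-month stability of true competence:

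| Stability | Observed r .21–.23 | .35–.39 | .49–.54 |
|---|---|---|---|
| 1.0 | 18–30% | 46–70% | 80–96% |
| .8 | 9–16% | 18–39% | 36–72% |
| .6 | 7–10% | 11–20% | 17–41% |

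Adding the t=1 rate at stability 1.0 gives 7–10%, 13–18% and 29–44%. Over the whole grid the range is about 6% to 44%. It does not return to 5% because the t=1 rate is itself noisy. With zero baseline correlation both models give about 5%. With a near-perfectly reliable VAS and stability .8 or lower, the planned model gives about 5–7%.

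**Cost in power.** With a true path b of .3, a t=1 to t=3 path of .5 and g=.2, power after adding the t=1 rate is about .985.

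**The case against.** **The text may already include it.** The plan does not say what *baseline* refers to, and in Hypothesis 1 the same term means the outcome's baseline. A reader might infer that the plan definitely adjusts for baseline competence alone. The documents do not settle that, and the site and randomisation-unit terms apply as well. What stands is that the wording sits in the clause on the mediator, so competence is the natural reading, and the t=1 rate is not named. If the sponsor meant it to be included, the text still has to say so.

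**The bias is conditional.** A reader might infer that habit will be counted as mediation. That needs a habit-competence link left over after baseline adjustment. The pilot correlation has no stated size, and it fits the plan's own causal theory equally well. This objection is correct.

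**The high percentages are a worst case.** The 80–96% row requires true competence to be perfectly stable over a year apart from a uniform shift by arm. The plan says VAS self-efficacy measures are reliable, without a figure. The 0.8 SD for path a is also an assumption, because Power, Hypothesis 3 does not say whether the large changes it expects are between arms. If path a were 0.3 SD between arms, it would be detected only about 65% of the time, and .65 × 96% is about 62%. All of this stands, but inflation remains over most of the grid.

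**Knowledge is a different matter.** Because Aim 2 names knowledge too, a reader might infer that omitting it biases Hypothesis 4. The plan deliberately makes competence its target mechanism. Knowledge at 12 months is affected by arm, so it is a possible second mediator, not a baseline confounder. False credit would need knowledge both to drive prescribing and to feed competence, and the documents quantify neither. What stands is that no specified analysis links knowledge to prescribing, although Aim 2 asks for it.

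**Aim 2 already speaks of association.** It does, but the Hypothesis 4 rationale describes the mediator as acting on the outcome.

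**Conclusion.** The point holds in conditional form. Hypothesis 4 does not define *baseline* and does not name the t=1 clozapine rate. Path b is not randomised, so prior habit can be credited to competence when a single noisy VAS does not fully absorb it.

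The size cannot be fixed from the documents. The range of about 7% to 96% as planned, and about 6% to 44% with the t=1 rate added, rests on the assumed correlations, reliabilities, stability and path a. No single value in it should be quoted as the trial's error rate. The t=1 rate reduces the problem without removing it, so a sensitivity analysis is also needed.

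This is a secondary mechanism analysis. The change is worth making because the variable is already held and the cost is small. The missing knowledge analysis is a separate and weaker point: a gap against Aim 2, not a demonstrated bias.

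**What to change.** In the Hypothesis 4 paragraph:

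1. Define *baseline* as baseline competence plus the prescriber's t=1 clozapine rate, and enter both in the mediator equation and the outcome equation. For the persistence outcome, say that the t=1 rate is only a proxy for prescriber habit.
2. Describe any indirect effect as association-based, and pre-specify a sensitivity analysis for residual confounding of the competence-outcome path.
3. State the scale of the 0.3 paths in the power statement.

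Separately and secondarily, add a supportive model with 12-month knowledge, adjusted for baseline knowledge, as a second mediator. Competence stays the pre-specified Hypothesis 4 mediator.

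The cost is SAP wording and a slightly wider interval for the indirect effect. No new data collection is needed. Prescribers not practising in the Maryland public system before the intervention will lack a t=1 rate and must be handled under the plan's missing-data section, which should say so.
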